#### b. Secondary Objectives

- To assess the viral load in the nasopharynx and oropharynx before and after application of 0.6% PVP-I of participants of this study.
- To assess the duration of effectivity of 0.6% PVP-I on mucosal surface of participating COVID-19 patients by testing consecutive sample hourly upto 4hr.
- To estimate the shelf-life and stability of 0.6 % PONS.
- To characterize raw materials and impurities for product development and quality control/ assurance
- To measure the safety level of  $0.6\% \underline{PONS}$  by biochemical analysis of participants blood & urine

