## Methodology

#### Study design

It will be a Multicentre, Single blind, Randomized Controlled Trial.

The participant will be divided into three groups namely Group A (384 intervention group and 384 control group), Group B (20 patient) and Group C (10 healthy person).

**Group A** Number of participants 768 COVID-19 positive, moderately ill admitted patient who will receive intervention once (2 puff 0.6% PVP-I in each nostril and 2 puff inside mouth).

Step 1: Enrollment of the study populations by applying inclusion and exclusion criteria

Step 2: Randomization to allocate experimental and controlled group by using table of random number

Step 3: Application of 0.6% PVP-I spray to experimental group and distilled water to control group

Step 4: Follow up (waiting for 2-5 minutes)

Step 5: Collection of nasopharyngeal and oropharyngeal sawab for RT-PCR test for both group

Step 6: Observation of the patients for 30 minutes for possible early adverse effects (if any) and subsequent management (if needed).

Step 7: Analysis data collection, data processing and analysis by using SPSS software.

**Group B** Number of participants 20 asymptomatic to mild COVID -19 patients to whom after single time application of PVP-I oro-nasal spray, RT-PCR test will be done hourly for 4 hours in a single day (to assess the duration of effectiveness of PVP-I oronasal spray).

Step 1: Selection of 20 patients randomly with no or mild symptoms and obtain their consent for the further tests.

Step 2: Collection of 2nd, 3rd and 4th sample from nasopharynx and oropharynx hourly

Step 3: Data collection, data processing and analysis by using SPSS software

**Group C** Number of participants 10 healthy individual who accept intervention 0.6% PVP-I oronasal spray 3-4 hours interval but not more than 4 times a day for 30 days.

Step 1: Selection of 10 healthy volunteers randomly who will be selected for using 0.6% PVP-I Oro-Nasal spray 2 puff inside both nostrils and mouth 3 to 4 times a day for one month.

Step 2: Collection of blood & urine of participants on day 0, 10, 20, 30 for determination of any change in biochemical marker (thyroid, kidney and liver functions will be done)

Step 3: Data collection, data processing and analysis by using SPSS software

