#### N.B.

• Patient with moderate symptoms are normally get admitted in Hospital, who will be included in Group-A.

The intervention Group-A will receive Oronasal spray containing PVP-I and control group will receive distilled water containing oronasal spray.

As all participants of Group-A (asymptomatic, mild, moderate) are included in the study, so they will receive the same treatment (PONS)

- Asymptomatic and mild patients having co-morbid conditions are also admitted in Hospital who will be included in Group-B.
- For Group-C Participants, pre-intervention investigation will be done (FT3, FT4 TSH etc).

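### The before/after viral-load objective has no designated pre-spray value in Groups A and B, and Group B's 1st sample is neither defined nor timed

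*Protocol*

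**What the plan says.** The Protocol (Objectives of the study, b. Secondary Objectives) sets two aims that depend on when samples are taken. One is "To assess the viral load in the nasopharynx and oropharynx before and after application of 0.6% PVP-I of participants of this study". The other is the duration of effect in COVID-19 patients, "by testing consecutive sample hourly upto 4hr". The N.B. after the study design makes the RT-PCR Ct value the measure of viral load and gives no time point for it.

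**Group A** (Methodology, Study design): enrolment, randomisation, spray or distilled water, a wait of 2-5 minutes, then Step 5, "Collection of nasopharyngeal and oropharyngeal sawab for RT-PCR test for both group". No other swab is listed.

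**Group B** (same section): after one application, "RT-PCR test will be done hourly for 4 hours in a single day". Step 1 has the investigators "obtain their consent for the further tests". Step 2 lists the 2nd, 3rd and 4th "sample from nasopharynx and oropharynx hourly". The 1st sample is not described, and the spray is not a numbered step.

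**Group C** has an explicit starting value: "Collection of blood & urine of participants on day 0, 10, 20, 30", and the N.B. under Selection Criteria adds that "pre-intervention investigation will be done".

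For Groups A and B, the only RT-PCR that must precede the spray is the qualifying one: a positive result within 24 hours (Inclusion Criteria). The section on demographic and baseline characteristics lists race, gender, age, height and weight. SAP section 2 lists general tests and ties none of them to a baseline.

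**The concern.** A before/after objective needs a stated starting value, and the text gives none for the two groups in which viral load is measured. Where the authors wanted a pre-intervention value they wrote it down, as in Group C, so the silence for Groups A and B leaves the objective open.

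The stakes differ by group. Group A has a randomised control arm, so a post-spray comparison needs no baseline to be valid. What is lost is the before/after result, any planned look at whether the arms started with similar viral load, and the precision that a baseline covariate could bring. Group B has no control arm and is the only source for the duration objective. Its result depends on which earlier value is used as the reference and on whether a 4 h sample exists. A 4 h swab that was not taken cannot be recovered, and three hospitals could read Step 2 differently.

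**Working it through.** **The plan's own figure.** n = Z²pq/d² = 1.96² × 0.5 × 0.5 / 0.05² = 384.16, so 384 per arm and 768 in Group A. The figure reproduces. The point does not turn on it.

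**Group A timeline.** The spray is Step 3, the wait Step 4 and the swab Step 5. Listed swabs before the spray: 0. Listed swabs after it: 1. Followed literally, the steps give no before/after pair unless the qualifying Ct is brought in, and no section says that it is.

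**Group B timeline.** Take hourly spacing, with the first hourly sample 1 h after the spray. The possible meanings of the 1st sample are:

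| 1st sample is | Samples 2-4 fall at | 4 h point | Value before the spray |
|---|---|---|---|
| the qualifying test | 1, 2, 3 h | missing | qualifying test, not designated |
| a same-day pre-spray swab | 1, 2, 3 h | missing | that swab, not listed |
| a swab minutes after the spray | about 1, 2, 3 h | missing | qualifying test, not designated |
| a swab at 1 h | 2, 3, 4 h | present | qualifying test, not designated |

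Step 2 lists 3 × 20 = 60 samples. Testing at 1, 2, 3 and 4 h needs 4 × 20 = 80. The gap of 20 is one sample per patient. In the last row it closes, because the unlisted 1st sample is the 1 h sample. In the other rows it is the 4 h sample of all 20 patients.

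**Precision in Group A (illustration).** The documents do not give the correlation r between qualifying and post-spray Ct, nor the share u of post-spray samples that are undetected. Both are assumptions here. Adjusting for the qualifying Ct lowers the variance of the arm difference by k·r². With Ct values bivariate normal, undetected values set at the cycle limit c, and the same u in both arms, k = P(Y<c)² / Var(min(Y,c)).

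| u | k | r = 0.3 | r = 0.5 | r = 0.7 |
|---|---|---|---|---|
| 0 | 1 | 9.0% | 25.0% | 49.0% |
| 0.3 | 0.869 | 7.8% | 21.7% | 42.6% |
| 0.5 | 0.733 | 6.6% | 18.3% | 35.9% |

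For example, at u = 0.5 the limit is the mean, so k = 0.25 / (0.5 − 1/(2π)) = 0.25 / 0.3408 = 0.733. Missing qualifying Ct values lower the gains further. If the spray itself raises Ct, u will differ between arms and the lower rows are only approximate.

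**The case against.** The strongest reply is that this is loose drafting. Numbering a 2nd, 3rd and 4th sample presupposes a 1st; if that is at 1 h, the steps agree with hourly testing to 4 h. Every Group A and B patient also has a positive RT-PCR within 24 hours, which could serve as the earlier value. The section on data collection says that participants' investigation papers will be used, and the case report form (Annexure 3) is not in the supplied text, so the qualifying Ct may well be recorded. Omitting ANCOVA is not an error.

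Most of this stands, and it rules out three stronger conclusions that a reader might draw:

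- *Group A's comparison is biased.* It is not. Both arms are swabbed at the same point after randomised treatment.
- *No baseline viral load is collected.* This cannot be shown. What the text shows is that no section designates one.
- *Group B's steps cannot be squared with testing to 4 h, or no reading gives both an earlier value and the full series.* The 1 h reading squares them, and with the qualifying test it supplies both.

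What the reply does not settle is which reading applies. A Ct on a form is not thereby the reference or part of the analysis, and it does not time Group B's 1st sample. Nor is the qualifying test an easy reference in Group B. It may be up to 24 hours old, it selected patients for being positive, and the Inclusion Criteria fix no common assay or swab site. With no control arm, regression to the mean and natural change can look like an effect of the spray.

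**Conclusion.** The point holds as an unmet specification, and it should be corrected. The objective promises viral load before and after the spray, and neither document names the earlier value for Groups A and B. In Group B the 1st sample is undefined, which puts the 4 h point at risk in all 20 patients on three of the four readings and in none on the fourth.

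In Group A the main randomised comparison is untouched. The possible gain in precision runs from 9% to 49% at assumed r of 0.3 to 0.7 with every Ct observed, and is smaller with undetected or missing values. These percentages illustrate the gain; they do not measure the defect. The width of a confidence interval for the mean change in 20 patients does not measure it either, because naming the reference leaves that width unchanged.

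Confidence is moderate, because the case report form was not available.

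**What to change.** **Group A.** Record the qualifying Ct, where the laboratory reports it, and the time since that test. Add it by arm to the baseline table. Analyse post-spray Ct by ANCOVA adjusted for it, with a rule fixed in advance for undetected and missing values. Report the result as the baseline-adjusted difference between arms, and word the objective for Group A to match, since this is a randomised contrast and not a within-patient change. Cost: one or two form fields (none if Annexure 3 already has them), one covariate, and some missing Ct values.

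**Group B.** Reconcile Step 2 with the stated hourly testing by listing samples at 1, 2, 3 and 4 h after the spray. That is 80 samples: 20 more than Step 2 lists and none beyond those already promised. Name the reference. If it is the qualifying test, state its possible age of up to 24 hours, the selection on positivity, the possible difference in assay and the lack of a control arm, and limit the conclusion to the trend across 1-4 h.

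**Optional.** A same-day pre-spray swab in Group B (20 swabs) would give a cleaner reference. The same in Group A would take 768 and is not needed for the randomised comparison.

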## **Objectives of the study**

#### a. Primary Objective

To assess the virucidal efficacy of 0.6% PVP-I against SARS-CoV-2 in nasopharynx and oropharynx in order to use:

- To prevent viral infection before exposure while visiting and treating COVID-19 patients, attending public gatherings, using public transport etc.
- To prevent viral infection after exposure to COVID-19 patients
- To reduce viral load in nasopharynx and oropharynx of COVID-19 patients which is supposed to reduce viral transmission through respiratory route

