## Selection Criteria Selection of Participants : For Group A and Group B

#### **Inclusion** Criteria

- 1. Hospital admitted patients tested positive COVID-19 within 24 hours in the laboratory by RT-PCR.
- 2. Patients with asymptomatic, mild to moderate illness of COVID-19.
- 3. Age group 18 year and above.
- 4. Consent of the patients, wish to be included in the study willingly.

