## Endpoints

#### **Primary Endpoints:**

• Virucidal efficacy of 0.6% PVP-I against SARS-COV-2 virus which infect oropharyngeal and nasopharyngeal mucosa of humans.

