## 2. Statistical Analysis tools

Data analysis software	: Statistical Package for the Social Sciences (SPSS)
Descriptive statistical parameter	: Mean, Medium, Mode, Standard Deviation, Percentage,
	Frequency
Inferential statistics	: Chi-square test, t-tes, F-test, Anova, Correlation
Confidence Interval	: 95%

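### The viral-load objective is worded as before versus after PVP-I, and neither document commits to comparing Ct between the randomised PVP-I and distilled-water arms

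*Protocol*

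**What the plan says.** The first of the protocol's Secondary Objectives is "To assess the viral load in the nasopharynx and oropharynx before and after application of 0.6% PVP-I of participants of this study". This is the only text in either document that states a contrast for viral load, and it does not mention the control arm.

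Other places where a comparator might have been named do not name one:

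- The Primary Objective has a viral-load element, "To reduce viral load in nasopharynx and oropharynx of COVID-19 patients which is supposed to reduce viral transmission through respiratory route", with no reference treatment.
- The Primary Endpoint is "Virucidal efficacy of 0.6% PVP-I against SARS-COV-2 virus which infect oropharyngeal and nasopharyngeal mucosa of humans", with no measure, time point or contrast.
- The notes after the Study design make Ct the semiquantitative measure of viral load (a higher Ct means less viral material), but do not say how arms are compared.
- The protocol's Data Analysis section lists generic tests and promises a plan that takes the objectives into account. SAP section 2 gives only "Chi-square test, t-tes, F-test, Anova, Correlation" and a 95% confidence level, and ties no test to any objective.

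The design does provide a control: "It will be a Multicentre, Single blind, Randomized Controlled Trial". In Group A, 384 patients per arm are randomised, with "Application of 0.6% PVP-I spray to experimental group and distilled water to control group". Both arms are swabbed after a wait of 2 to 5 minutes. The Group A steps list no swab just before spraying. The only earlier PCR that can be identified is the entry test: "Hospital admitted patients tested positive COVID-19 within 24 hours in the laboratory by RT-PCR".

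**The concern.** A change measured within PVP-I recipients contains the drug effect plus everything else that differs between the two samples. Which non-drug sources are present depends on which sample serves as the before value:

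- **Rinsing or dilution by the sprayed liquid** enters in either case, because the spray always falls between the two samples.
- **Course of infection** matters if the before value is the eligibility PCR, which may be up to 24 hours old. Over 2 to 5 minutes it would be negligible.
- **Regression to the mean** also applies if the eligibility PCR is used. Entry requires a positive result on that test, so a repeat would tend towards higher Ct, which looks like a fall in viral load. A fresh swab just before spraying, not used for selection, would not carry this.

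The water arm shares these sources, so the difference between arms removes them on average. An analysis that took the objective literally would not. With 384 patients, even a small shared shift could reach significance and be reported as virucidal efficacy. The protocol's Utilization of Results section intends to use the findings to encourage public use of the spray, so the contrast should be fixed beforehand.

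**Working it through.** **The plan's own figure.** The sample-size formula gives n = Z²pq/d² = 1.96² × 0.5 × 0.5 / 0.05² = 384.16, so the stated 384 is reproduced. It is a precision formula for a single proportion, applied to each arm. It contains no Ct SD, target difference or power, so it does not indicate which Ct contrast is intended.

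**Inputs.** From the documents: 384 per arm, two-sided 5% level (Z = 1.96). Assumed, because the documents give no such figures: SD of within-patient change 4, 5 or 6 Ct; a non-drug shift of 0.5 or 1 Ct common to both arms; a true PVP-I effect of zero.

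**One-arm before/after test.** SE = SD/√384, z = shift/SE, and the probability of a significant result is Φ(z − 1.96) plus a negligible opposite tail.

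| SD of change | SE | z, shift 0.5 | significant | z, shift 1 | significant |
|---|---|---|---|---|---|
| 4 | 0.204 | 2.45 | 69% | 4.90 | 99.8% |
| 5 | 0.255 | 1.96 | 50% | 3.92 | 97.5% |
| 6 | 0.306 | 1.63 | 37% | 3.27 | 90.4% |

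Wider assumptions were also tried: per-sample SD 3 to 7 Ct and before/after correlation r from 0.3 to 0.8, where SD of change = SD × √(2(1 − r)). The rate is then 9% to 73% for a 0.25 Ct shift, 22% to 99.9% for 0.5 Ct, and 66% to essentially 100% for 1 Ct.

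**Between-arm test on the same data.** A shift common to both arms cancels in the difference. In 10,000 simulated trials per setting (per-sample SD 5, correlation 0.5, so SD of change 5), the one-arm and between-arm rejection rates were 49.6% and 5.0% for a shift of 0.5, 97.6% and 5.4% for a shift of 1, and 100% and 5.1% for a shift of 2.

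**What the between-arm comparison can detect.** Unadjusted, with 80% power: (1.96 + 0.84) × √(2/384) = 0.20 SD. With 90% power: (1.96 + 1.28) × √(2/384) = 0.23 SD. Adjusting for an earlier Ct multiplies the SE by √(1 − ρ²), where ρ is its assumed correlation with the post-spray Ct: 0.954 at ρ = 0.3, 0.866 at 0.5 and 0.714 at 0.7, a reduction of 5% to 29%. At ρ = 0.5 the 80%-power difference becomes 0.202 × 0.866 = 0.175 SD.

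**The case against.** The strongest reply is that an objective says what is to be assessed and is not an analysis specification. No text orders a paired test in the PVP-I arm. The listed t-test could equally be a two-sample test, and everything about the design (randomisation, a water control, swabs in both arms, the sample size applied to each arm) points to a between-arm comparison. The Group A steps do not even list a pre-spray swab to pair with. This stands: a reader might infer that the plan has chosen an uncontrolled paired analysis, and the documents do not support that. They leave the contrast open, and the only wording that touches it is the uncontrolled one.

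A reader might also infer that the weakness is the same whichever sample serves as the before value. It is not: disease course and regression to the mean depend on using the eligibility PCR, and only spray rinsing clearly remains with a fresh pre-spray swab.

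Third, the rejection rates rest wholly on assumed values, so they are not an estimate of this trial's error rate. That also stands.

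Fourth, covariate adjustment is a gain in precision, and leaving it out is not an error. Agreed; the point concerns the missing comparator.

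Finally, this may look like one instance of a wider gap, since the SAP ties no test to any objective. It is, but here the existing wording points to a specific uncontrolled contrast, so filling that gap by following the objectives would not by itself repair it.

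**Conclusion.** The point holds in limited form: the stated contrast for viral load omits the water arm and no other text commits to using it, although the trial will collect the control data. The rejection rates of 37% to 69% (0.5 Ct shift) and 90% to 99.8% (1 Ct shift), against a nominal 5%, show how an analysis following the objective literally could mislead. They assume no drug effect, a shift equal in both arms and an SD of change of 4 to 6 Ct, so they illustrate the risk and do not measure an error already made.

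The control has two limits. It protects only Group A, because the 20 Group B patients are all sampled after PVP-I with no control arm. And it removes only what the arms share, so an iodine-specific effect on the swab or assay, if there is one, would remain in the between-arm difference.

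**What to change.** - **Objective.** Restate it for Group A as the difference between PVP-I and distilled water in post-spray Ct at 2 to 5 minutes, reported with a 95% CI.
- **SAP.** Make this between-arm comparison the efficacy analysis. Use analysis of covariance of post-spray Ct on arm, with the eligibility RT-PCR Ct as covariate where it is recorded. Without it, the unadjusted between-arm comparison remains valid.
- **Undetectable results.** Prespecify the value given to a post-spray sample with no detectable virus, for example the assay's cycle limit. Add a rank-based or detectable/undetectable comparison as a sensitivity analysis.
- **Descriptive only.** Report within-arm changes, and all Group B results, without an efficacy claim.

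The cost is wording in two documents and transcription of the eligibility Ct; no extra patients or swabs are needed. There are two small downsides. The reported reduction may be smaller than the raw before/after change. The protocol also says only that entry patients tested positive, so a Ct may not always be available, and it may come from different assays at the three hospitals, which would weaken its value as a covariate.

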## **Study Rationale**

Povidone Iodine or PVP-I (Iodine with water soluble polymer Polyvinylpyrolidone) is a proven and time trusted antiseptic agent having best possible (99.99%) virucidal effect in 0.23% concentration. It acts against many/maximum viruses including SARS-CoV and MERS-CoV due to it's nonspecific mode of action in virus killing and shows no resistance. Baley et. al, 2020, proposed that 0.5% PVP-I could safely be used in nasal spray to kill SARS-CoV-2 virus [4, 6]. A previous study showed that 1.0% PVP-I used in gargle/mouthwash could reduce the viral titer of  $\geq$ 4 log 10 by 99.99% in case of MERS-CoV infection [4]. Even in higher concentration of PVP-I (2.2% to 4.4 % liposomal preparation) was proved safer to apply as a nasal spray for antimicrobial activity [5].

Corona virus is transmitted via respiratory droplets or aerosol, produced from sneezing or coughing of infected persons to healthy individual through mouth, nose and eye. PVP-I gargle/spray used in throat and nose are shown to have board spectrum antimicrobial activity and may have preventive effect on SARS-CoV-2. Though wearing masks and social distancing can significantly reduce transmission and spread but these practice have not been universally adopted. As we are eagerly waiting for a definition treatment and an effective vaccination to contain and pervert the spread of SARS-COV-2, additional strategies are required to reduce transmission. 0.6% PONS which will directly treat the major sites of reception of transmission of SARS-Cov-2 virus may provide an additional level of protection against this virus. This study aims to evaluate virucidal efficacy of 0.6% PVP-I against SARS-CoV-2 amongst humans and its safety that is expected to contribute to save lives during this COVID-19 pandemic.

